OCT	Optical Coherence Tomography
PVD	Posterior Vitreous Detachment
PVL	Pneumatic Vitreolysis
SADE	Serious Adverse Device Event
SAE	Serious Adverse Event
SD	Standard Deviation
UADE	Unanticipated Adverse Device Effect
VMT	Vitreomacular Traction
VMA	Vitreomacular Adhesion

PROTOCOL SUMMARY

PARTICIPANT AREA	DESCRIPTION
Title	Single-Arm Study Assessing the Effects of Pneumatic Vitreolysis on Macular Hole
Précis	Eyes with vitreomacular traction (VMT) and full-thickness macular hole (MH) will be enrolled into a non-randomized cohort treated with PVL to determine the proportion with VMT release and MH closure and to assess factors associated with success.
Investigational Device	Intraocular gas (C ₃ F ₈) injection
Objectives	To obtain estimates of the proportion of eyes with MH closure of the inner retinal layers for eyes with VMT and full-thickness MHs treated with PVL.
Rationale	Understanding the rates of VMT release and MH closures in eyes with full-thickness MH treated with PVL is of interest. Surgery would result in nearly 100% hole closure and VMT release, making vitrectomy a poor control group choice. Spontaneous resolution of MH is highly unlikely, making an observation arm unnecessary. Therefore, these eyes will be enrolled into a non-randomized cohort treated with PVL to assess the outcomes of treatment.
Study Design	Single-arm study
Number of Sites	Approximately 50 sites
Endpoint	
Primary Outcome: Proportion of eyes with MH closure of the inner retinal layers without rescue treatment at 8 weeks.
 
Key Secondary Outcomes: proportion of eyes with central VMT release without rescue treatment, proportion of eyes with rescue treatment, mean change in visual acuity
 
Key Safety Outcomes: retinal tear, retinal detachment, traumatic cataract, cataract extraction, vitreous hemorrhage, intraocular pressure (IOP) increase, and endophthalmitis.

Population	
Key Inclusion Criteria
 
 • Age \geq 18 years. • Able and willing to avoid high altitude until gas resolution (approximately 6 to 8 weeks) • For phakic patients, able and willing to avoid supine positioning until gas resolution (approximately 6 to 8 weeks) • Able and willing to position face down for at least 50% of the time for at least 4 days post-injection • At least 1 eye with:

PARTICIPANT AREA	DESCRIPTION

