- 219 e. High level of myopia (spherical equivalent of -8.00 diopters or more myopic if phakic, or 220 retinal abnormalities consistent with pathologic myopia if phakic or pseudophakic)
- 221 f. History of prior gas injection, ocriplasmin injection, or intraocular injection for any reason
- 222 g. History of prior vitrectomy
- 223 h. History of uncontrolled glaucoma
 - 224 • *Intraocular pressure must be < 30 mmHg, with no more than one topical glaucoma 225 medication, and no documented glaucomatous field loss for the eye to be eligible*
- 226 i. History of major ocular surgery (including cataract extraction, scleral buckle, any intraocular 227 surgery, etc.) within prior 4 months or major ocular surgery anticipated within the next 6 228 months following enrollment
- 229 j. History of YAG capsulotomy performed within 4 months prior to enrollment
- 230 k. Aphakia or anterior chamber intraocular lens
- 231 l. Exam evidence of severe external ocular infection, including conjunctivitis, chalazion, or 232 substantial blepharitis
- 233 m. Uveitis
- 234 n. Retinal history or pathology that might predispose an eye to an increased risk of retinal 235 detachment from the procedure
 - 236 • *Untreated retinal tears, not retinal holes, are an exclusion. It is up to the investigator to 237 determine whether extent of lattice degeneration or other pathology might increase the 238 risk of retinal detachment*
- 239 o. Any contraindication to paracentesis (e.g., history of narrow angle glaucoma)
- 240 p. Lenticular or zonular instability

241 **2.3 Screening Evaluation and Baseline Testing**

242 After informed consent has been signed, the potential participant will be evaluated for study 243 eligibility through the elicitation of a medical history and performance of an ocular examination 244 by study personnel to screen for exclusionary conditions.

245 Individuals who do not initially meet study eligibility requirements may be rescreened at a later 246 date per investigator discretion.

247 All testing does not need to be completed on the same day provided it is within the windows 248 specified below. Reading Center confirmation of VMT with full-thickness macular hole on OCT 249 must be completed prior to enrollment.

250 **2.3.1 Baseline Testing Procedures**

251 The following procedures are needed to confirm eligibility and/or to serve as baseline measures 252 for the study:

253 • If a procedure has been performed using the study technique and by study certified

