254 personnel as part of usual care, then it does not need to be repeated specifically for the
255 study if it was performed within the defined time windows specified below.

256 • The testing procedures are detailed in the DRCR Retina Network Procedures Manuals.
257 Visual acuity testing, ocular exam, and OCT will be performed by DRCR Retina
258 Network certified personnel.

259 1. Self-reported demographics (date of birth, sex, race, and ethnicity)

260 2. Medical history (pre-existing medical conditions, concomitant medications, as well as ocular
261 diseases, surgeries, and treatments)

262 • Medical history will be obtained by medical charts if available at the enrolling site;
263 otherwise, it will be self-reported

264 3. Electronic-ETDRS visual acuity testing at 3 meters using the Electronic Visual Acuity Tester
265 (including protocol refraction) in each eye (*within prior 8 days*)

266 4. Spectral-Domain OCT using Zeiss Cirrus or Heidelberg Spectralis on each eye (*within prior
267 8 days*)

268 • OCT scans of the study eye will be promptly sent to the central reading center for
269 grading and a participant cannot be enrolled until reading center confirmation of
270 eligibility has been received.

271 5. Ocular examination on each eye including slit lamp, measurement of IOP, lens assessment,
272 and dilated ophthalmoscopy (*within prior 8 days*)

273 • Scleral depression to rule out any retinal tears pre-operatively will be required for the
274 baseline eye exam to confirm eligibility.

275

CHAPTER 3: BASELINE TREATMENT

276 **3.1 Treatment**

277 The C₃F₈ gas injection must be given on the day of enrollment.

278 **3.2 Injection Procedure**

279 **3.2.1 Intravitreous Injection Technique**

280 The injection is preceded by a povidone iodine prep of the conjunctiva. A subconjunctival
281 injection of lidocaine may be administered at the discretion of the investigator. The injection will
282 be performed using sterile technique. Pre-injection paracentesis should be considered due to the
283 4x expansion of C₃F₈ gas and the associated risk of shallowing of the anterior chamber.
284 However, the choice of when or whether or not to do a paracentesis is ultimately at the
285 investigator's discretion. The full injection procedure is described in the protocol-specific study
286 procedures manual. Topical antibiotics in the pre-, peri-, or post-injection period should not be

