 - 31 ▪ MH closure with central VMT release with rescue treatment
 - 32 ▪ MH closure without central VMT release with rescue treatment
- 33 • Mean change in visual acuity letter score from baseline at 8 and 24 weeks.

34 • Proportion of eyes with at least 10-letter gain (increase) in visual acuity from baseline at
35 8 and 24 weeks.

36 • Proportion of eyes with at least 10-letter loss (decrease) in visual acuity from baseline at
37 8 and 24 weeks.

38 • Proportion of eyes receiving rescue treatment before the 8-week visit.

39 • Proportion of eyes receiving rescue treatment before the 24-week visit.

40 ○ For purposes of description only, the following will be tabulated without
41 statistical comparison:

42 ■ Proportion of eyes receiving rescue treatment before the 24-week visit or
43 for which rescue treatment is planned at the 24-week visit and medical
44 records confirm rescue treatment occurred within the subsequent 12
45 weeks.

46 ■ Type of rescue treatment.

47 **1.2.3 Exploratory Outcomes:**

48 • Proportion of eyes with MH closure of the inner retinal layers with outer retinal lucency*
49 without rescue treatment at 8 and 24 weeks.

50 • Proportion of eyes with ellipsoid zone* integrity at 8 and 24 weeks.

51 ○ Both ellipsoid zone integrity within 1 mm of the center of the macula and at the
52 foveal center will be analyzed

53 *Determined by masked grader at the central reading center.

54 **1.3 Analysis Cohorts**

55 • Intention-To-Treat (ITT) Analysis Cohort: all enrolled participants irrespective of
56 treatment received.

57 • Safety Analysis Cohort: all enrolled participants irrespective of treatment received.

58 • Per-Protocol Analysis Cohort: only participants who complete the initial treatment (PVL)
59 and do not receive any non-protocol treatments during follow up. Vitrectomy performed
60 according to the criteria in section 4.2.1 of the protocol is considered per protocol and
61 eyes receiving this procedure will be included in the per-protocol cohort.

62 The primary analysis will follow the ITT principle and include all enrolled participants.

63 A per-protocol analysis will be performed to provide additional information regarding the
64 magnitude of the treatment effect. The per-protocol analysis will only be performed if at least
65 10% of enrolled participants would be excluded by these criteria (e.g., 5 or more participants if
66 exactly 50 are enrolled).

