67 The ITT analysis is considered the primary analysis. If the results of the per-protocol and ITT
68 analyses give inconsistent results, then the per-protocol analysis will be interpreted with caution.
69 In this scenario, exploratory analyses will be performed to evaluate possible factors contributing
70 to the difference.

71 **1.4 Analysis of the Primary Efficacy Outcome**

72 The primary outcome of MH closure of the inner retinal layers without rescue treatment through
73 8 weeks is a binary variable that is graded by the central reading center. The proportion of eyes
74 meeting the primary outcome will be determined and the 95% Wilson (score) confidence interval
75 will be calculated.¹⁻³

76 Since the chance of re-opening after closure before 8 or 24 weeks is highly unlikely, an eye with
77 MH closure of the inner retinal layers without rescue treatment at any time prior to 24 weeks will
78 be considered to have met the outcome through 24 weeks if the participant is lost to follow-up.
79 Similarly, any eye receiving rescue treatment prior to 24 weeks will be considered not to have
80 met the outcome through 24 weeks.

81 Multiple imputation will be used to impute missing data for eyes lost to follow-up that did not
82 have prior MH closure or rescue treatment documented. The imputation model will include MH
83 status at 1, 4, 8, and 24 weeks.

84 A sensitivity analysis will be conducted using the same approach as above, but without multiple
85 imputation (i.e., complete-case analysis).

86 **1.5 Analysis of the Secondary and Exploratory Outcomes**

87 The ITT analysis cohort will be used for all secondary and exploratory outcomes.

88 **1.5.1 Secondary Efficacy Outcomes**

89 There are two time-to-event outcomes to be evaluated through 24 weeks: (1) macular hole
90 closure of the inner retinal layers without rescue treatment and (2) central VMT release without
91 rescue treatment. Each of these outcomes will be graded by the central reading center. For each
92 outcome, a Kaplan-Meier curve will be constructed and the cumulative probability of the
93 outcome with 95% confidence interval will be estimated for the final time point. Data from eyes
94 not observed to meet the outcome or that receive rescue treatment will be censored on the date of
95 their final visit (not the date of rescue treatment). The analysis of central VMT release without
96 rescue treatment will be limited to eyes with central VMT at baseline. Because the chance of re-

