124 tabulated in a listing of each reported Medical Dictionary for Regulatory Activities (MedDRA)
125 term and summarized over each MedDRA System Organ Class. All enrolled participants will be
126 included in safety analyses. Any events occurring between enrollment and study treatment will
127 be counted. The number of adverse events (ocular or systemic) considered related to treatment
128 will be tabulated.

129 **1.6.1 Ocular Adverse Events**

130 The frequency of each ocular adverse event occurring at least once per eye will be calculated.
131 The proportion of eyes experiencing each outcome will be calculated along with 95% Wilson
132 (score) confidence intervals. The following ocular adverse events are of primary interest:

- 133
 - Endophthalmitis
 - 134 ○ Retinal detachment
 - 135 ○ Retinal tear
 - 136 ○ Traumatic cataract
 - 137 ○ Cataract extraction in eyes phakic at baseline
 - 138 ○ Vitreous hemorrhage
 - 139 ○ Adverse intraocular pressure (IOP) events (composite outcome)
 - 140 ■ Increase in IOP \geq 10 mmHg from baseline (at a follow-up visit)
 - 141 ■ IOP \geq 30 mmHg (at a follow-up visit)
 - 142 ■ Initiation of medication to lower IOP that was not in use at baseline
 - 143 ■ Glaucoma procedure

144 **1.6.2 Systemic Adverse Events**

145 The frequency of each systemic adverse event occurring at least once per participant will be
146 calculated. The following systemic adverse events are of primary interest:

147

- Death

- Serious adverse event (at least one)

The following systemic adverse events are of secondary interest:

- For each MedDRA System Organ Class, proportion of participants with at least one serious adverse event

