1.11 Subgroup Analyses

Subgroup analyses, i.e., assessments of effect modification, will be conducted to detect factors associated with the primary outcome. These analyses will be considered exploratory.

Subgroup analyses will be conducted using logistic regression. The risk difference for the subgroup factor (estimated with conditional standardization),⁴ 95% confidence interval (estimated with the delta method)⁴, and *P* value will be presented. To aid in interpretation of the risk difference, observed outcome proportions will be reported for each subgroup. Subgroup analyses will use data from eyes that complete the 8-week visit or have MH closure or rescue treatment prior to 8 weeks (i.e., complete case analysis as described in section 1.4).

The primary subgroup analysis will evaluate the effect of ERM presence within 1 mm of the center of the macula at baseline.

Secondary subgroup analyses will include ERM presence at the site of vitreous adhesion, lens status (phakic or pseudophakic), retinoschisis, subretinal fluid within 1 mm of the center of the macula, length of adhesion on OCT (less than or equal to 1500 microns or greater than 1500 microns), and diabetes status (has diabetes or does not have diabetes). Subgroups will be defined by the value at baseline.

There are no data to suggest that the treatment success will vary by sex or race/ethnicity. However, both of these factors will be evaluated in exploratory subgroup analyses as mandated by National Institutes of Health (NIH) guidelines.

Subgroup factors will be analyzed as categorical and continuous or ordinal variables where possible. Secondary and exploratory subgroup analyses will only be conducted if there are at

184 least 10 eyes in each subgroup. The primary subgroup analysis will be conducted regardless of
185 sample size.

186 **1.12 Multiple Testing**

187 There will be no adjustments made for multiple testing because this is a single-arm study without
188 treatment group comparisons. Only $P \leq .05$ will be considered of interest.

189 **1.13 Visit Windows for Analysis**

190 The analysis windows for visits will be defined according to Table 1. If multiple visits fall within
191 the same window, priority will be given to the protocol visit over unspecified visits. If there is no
192 protocol visit in the window, then the visit closest to the target date (but within the analysis
193 window) will be designated as the analysis visit. Visit windows will be filled in the following

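### Traumatic cataract is reported over all enrolled eyes, including pseudophakic eyes that cannot have it, while the next line limits cataract extraction to phakic eyes

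*SAP*

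**What the plan says.** SAP 1.6.1 sets one summary for every ocular event on its list: "The proportion of eyes experiencing each outcome will be calculated along with 95% Wilson" score limits. It names no denominator event by event. The default comes from SAP 1.3, "Safety Analysis Cohort: all enrolled participants irrespective of treatment received", and SAP 1.6 repeats that everyone enrolled enters the safety analyses. Each participant contributes one study eye.

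Two adjacent lines concern the lens. Traumatic cataract has no qualifier. The next reads "Cataract extraction in eyes phakic at baseline". Protocol 8.8 has the same two lines in the same form, and neither document restricts traumatic cataract anywhere else.

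On who can be enrolled, the only artificial-lens or missing-lens exclusion in Protocol 2.2.2 is "Aphakia or anterior chamber intraocular lens", so other pseudophakic eyes are eligible. SAP 1.11 plans for them: its lens subgroup is defined by "status (phakic or pseudophakic), retinoschisis" being the next factor listed. Traumatic cataract is prominent in the protocol summary: "Key Safety Outcomes: retinal tear, retinal detachment, traumatic cataract, cataract extraction, vitreous hemorrhage".

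**The concern.** An eye without its natural lens contributes to the traumatic cataract denominator but can never contribute to the numerator. Counting such eyes lowers the proportion and its upper limit relative to the eyes actually exposed to the risk. The bias runs only one way, towards reassurance.

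The plan recognises the principle elsewhere. It restricts cataract extraction to phakic eyes, and in SAP 1.5.1 the analysis of central VMT release without "rescue treatment will be limited to eyes with central VMT at baseline". Traumatic cataract is the exception, with no reason given.

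Protocol 1.4.1 puts the cataract risk from the injection below 1%, with a similar risk from paracentesis where one is done. Few or no events are therefore expected, and the upper confidence limit becomes the informative part of the result. A phakic patient or a treating physician would read a limit diluted by eyes not at risk, beside a cataract extraction line that is not diluted. The SAP revision history records early stopping for safety concerns with a smaller sample than planned, so readers are likely to look closely at the safety intervals.

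**Working it through.** **Inputs from the documents.** Planned size 50 eyes (Protocol 8.3.2); 95% Wilson intervals (SAP 1.6.1); smallest size tabulated in Protocol Table 1, 25 eyes.

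**Assumptions.** The share of eyes phakic at baseline is not given; 80%, 60% and 40% are used as illustrations. The final N is not given beyond being below plan; 50, 35 and 25 are used.

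**Formula.** For x events in n eyes, p = x/n and z = 1.96 (z² = 3.84):

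- centre = (p + z²/2n) / (1 + z²/n)
- half-width = z/(1 + z²/n) × √[p(1−p)/n + z²/4n²]

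**Check against the plan's own figures.** The documents state no precision for the lens outcomes. Protocol Table 1 does give half-widths for macular hole closure. At n = 50 and p = 50%, the half-width is 1.96/1.0768 × √(0.005 + 0.000384) = 13.4%, as printed. All nine cells of the table reproduce to 0.1 point with the Wilson formula. The simple Wald formula does not reproduce them (13.9% in that cell).

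**No events.** The upper limit reduces to z²/(n + z²). At N = 50 over all eyes it is 3.84/53.84 = 7.1%. Over 30 phakic eyes it is 3.84/33.84 = 11.4%.

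| N | All eyes | 80% phakic | 60% phakic | 40% phakic |
|---|---|---|---|---|
| 50 | 7.1% | 8.8% (n=40) | 11.4% (n=30) | 16.1% (n=20) |
| 35 | 9.9% | 12.1% (n=28) | 15.5% (n=21) | 21.5% (n=14) |
| 25 | 13.3% | 16.1% (n=20) | 20.4% (n=15) | 27.8% (n=10) |

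The ratio of the phakic-eye limit to the all-eyes limit is 1.23 / 1.59 / 2.26 at N = 50, 1.22 / 1.56 / 2.18 at N = 35 and 1.21 / 1.53 / 2.08 at N = 25.

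**One event.** The point estimate over all eyes equals the phakic-eye estimate multiplied by the phakic share.

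| N | All eyes | 80% phakic | 60% phakic | 40% phakic |
|---|---|---|---|---|
| 50 | 2.0% (0.4–10.5) | 2.5% (0.4–12.9) | 3.3% (0.6–16.7) | 5.0% (0.9–23.6) |
| 25 | 4.0% (0.7–19.5) | 5.0% (0.9–23.6) | 6.7% (1.2–29.8) | 10.0% (1.8–40.4) |

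If every eye is phakic, the two bases coincide and nothing changes.

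**The case against.** The strongest reply is that this is a choice of target, not a mistake. The plan declares an all-enrolled safety cohort and never says it will estimate traumatic cataract risk among phakic eyes. The risk of under 1% quoted in Protocol 1.4.1 is likewise not limited to phakic eyes. That stands as far as it goes: the all-eyes proportion is a valid risk per enrolled eye. It does not explain why the adjacent lens outcome uses a different base.

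The denominators are also inferred, since the SAP does not state them line by line. One could read the phakic qualifier as limiting only which extractions are counted. But a pseudophakic eye has no cataract to extract, so on that reading the qualifier would do nothing; a restricted denominator is the natural meaning.

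The size rests on assumptions, and the larger ratios need a 40% phakic share that nothing in the documents supports. This stands. So does the observation that every zero-event limit shown at N = 50, from 7.1% to 16.1%, is far above 1%, so neither base could confirm or refute the anticipated risk. A reader given the phakic count, which the extraction line already needs, could also recompute the figure, though the reported interval would still not be the at-risk one.

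Finally, one could add a phakic-only figure and keep the planned one, which avoids replacing a denominator after data review. That is a reasonable alternative. Little is lost by replacing, however: the all-eyes proportion can be recovered from the event count and total enrolment, and the change makes the reported result less favourable, so it is not open to suspicion of self-interest.

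**Conclusion.** The concern holds and is minor. Followed as written, the plan dilutes a safety proportion of primary interest, and its upper limit, with eyes that cannot have the event, and it does so inconsistently with the next line and with its own practice for VMT release.

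Under the assumed phakic shares the zero-event upper limit for phakic eyes is about 1.2 times the all-eyes limit at 80% phakic, 1.5 to 1.6 times at 60%, and 2.1 to 2.3 times at 40%. At N = 50 and 80% phakic the gap is only 1.6 points. The true size cannot be fixed from the documents.

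One of seven descriptive ocular outcomes is affected. Primary efficacy, the sample size and the stopping criteria do not depend on it.

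**What to change.** In SAP 1.6.1, give the traumatic cataract line the same phakic-at-baseline restriction as cataract extraction, and state that its denominator is the number of eyes phakic at baseline. Leave the other ocular events on all enrolled eyes. Because SAP version 2.0 was written after study data had been reviewed, record the edit in SAP 1.17.

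The cost is one phrase and one denominator in one table. Protocol 2.3.1 already requires "Ocular examination on each eye including slit lamp, measurement of IOP, lens assessment" at baseline, so no new data are needed. Protocol 8.1 describes Chapter 8 as a framework for the final analysis plan, and Protocol 10.2 ties IRB approval to protocol amendments and consent-form changes; on that basis an SAP-only edit should need neither an amendment nor IRB review, though the documents set out no specific review route for SAP changes. SAP 1.6.1 would then differ from Protocol 8.8, which can be aligned if the protocol is amended for another reason. The price in the results is a wider interval and a slightly less favourable figure.
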